8.2.4. Overview of Planned Other Safety Analyses

The safety analyses will be based on the Intent-To-Treat (ITT) population, unless otherwise specified in [Appendix 13: List of Data Displays](#). The safety displays to be created as part of the RAP include all the required and relevant displays identified as per the RAP Core Safety Reporting Template Version 1.0.

[Table 8](#) provides an overview of the planned analyses, with further details of data displays being presented in [Appendix 13: List of Data Displays](#).

Table 8 Overview of Planned Other Safety Analyses

Endpoint / Parameter/ Display Type	Absolute			Change from BL		
	Summary		Individual	Summary		Individual
	T	F	L	T	F	L
ECG						
ECG Findings	Y		Y			
Change from Baseline in ECG Values by Visit				Y		
Actual and Change From Baseline QTc(F) Values by Category	Y			Y		
Actual and Change From Baseline QTc(B) Values by Category	Y			Y		

Endpoint / Parameter/ Display Type	Absolute			Change from BL		
	Summary		Individual	Summary		Individual
	T	F	L	T	F	L
Vital Signs						
Change from Baseline in Vital Signs by Visits				Y		
Immunogenicity						
Immunogenicity (ADA and NAb results)	Y		Y			
Treatment Emergent ADA results	Y					

NOTES:

- T = Table, F = Figures, L = Listings, Y = Yes display generated, PCI = Potential Clinical Importance
- Summary = Represents TFL related to any summaries (i.e. descriptive statistics) of the observed raw data.
- Individual = Represents FL related to any displays of individual subject observed raw data.

8.2.4.1. Immunogenicity

Immunogenicity is a measure of the immune response to a therapeutic drug (e.g. a monoclonal antibody) resulting in generation of anti-drug antibodies. Clinical samples are tested in a sequence of binding anti-drug antibody (ADA) and neutralising antibody assays:

- a) Screening assay. Each sample is tested for the presence of anti-drug antibodies (ADA assay) and initially declared positive or negative according to assay cut-off criteria. Negative samples are not tested further. Positive samples are then tested in the confirmation ADA assay.
- b) Confirmation assay. Each positive sample from the screening assay is either confirmed positive in this assay (ADA assay), or is declared negative and are not tested further. Positive ADA samples are then tested in the titer assay and neutralisation (NAb) assay.
- c) Titration assay. Each positive sample from the ADA confirmation assay is serially diluted to provide a titre, corresponding to the highest dilution factor that still yields a positive test result.
- d) Neutralising assay. Each positive sample from the ADA confirmation assay is tested with the neutralising antibody assay and found as either positive or negative in this assay (NAb assay).

The mepolizumab ADA (screening/confirmation/titration) assay version 2011N122789 is performed at Alliance Pharma (method 120711M01.V02). The mepolizumab Nab assay version 2011n129752 is being performed within GSK.

- A table will be produced summarising the number and percentage of negative and confirmed positive subjects ADA samples by treatment group and visit in the ITT population. The table will also summarise the highest assay result obtained post-baseline for each subject.
- A similar table will also be produced summarising results for the neutralising antibody assay in the ITT Population, by treatment group and visit.

- An additional summary of treatment emergent positive confirmatory binding antibody assay and results in the subset of subjects who did not have a positive confirmatory binding antibody assay result prior to the first dose of study treatment will also be presented.
- All immunogenicity results (i.e. ADA screening and confirmatory assay results, titre values, neutralising antibody results and observed mepolizumab concentration) will be listed.

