	
• Incidence of immunogenicity

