8.2. Safety Analyses

8.2.1. Overview of Planned Analyses

The safety analyses will be based on the Intent-To-Treat (ITT) population, unless otherwise specified in [Appendix 13: List of Data Displays](#). The safety displays to be created as part of the RAP include all the required and relevant displays identified as per the RAP Core Safety Reporting Template Version 1.0.

Table 6 provides an overview of the planned analyses, with further details of data displays being presented in [Appendix 13: List of Data Displays](#).

Adverse events will be coded using the latest version of the Medical Dictionary for Regulatory Activities (MedDRA).

Table 6 Overview of Planned Adverse Event Analyses

Endpoint / Parameter/ Display Type	Absolute		
	Summary		Individual
	T	F	L
Exposure			
Number of treatments administered and time on-treatment	Y		Y
Adverse Events (AEs)			
Overview of Adverse Events	Y		
AEs by SOC and Maximum Intensity	Y		Y
Common Adverse Events by Overall Frequency ^[1]	Y		
All Drug-Related AEs by SOC and Maximum Intensity	Y		
AEs on the Day of Dosing	Y		
AEs by the Age Group (<18 year, ≥18 years)	Y		
AEs by Highest Antidrug Antibody Result At Any Time Post Baseline	Y		
Number of subjects & occurrences of common ^[1] non-serious AEs by SOC and PT	Y		
Subject Numbers for Individual AEs			Y
Relationship between AE SOCs, PT & verbatim text			Y
Serious and Other Significant AEs			
Fatal Serious AEs	Y		Y
Non-Fatal Serious AEs	Y		Y
Serious AEs by SOC	Y		
Reasons for Considering as a Serious AE			Y
Drug-Related Serious AEs by SOC and Maximum Intensity	Y		
AEs Leading to Withdrawal from Study / Permanent Discontinuation of Study Treatment by Overall Frequency	Y		Y
Number of Subjects and Occurrences of Serious, Drug-Related Serious, Fatal Serious, and Drug-Related Fatal Serious AEs	Y		
Adverse Events of Special Interest (AESI) (On-Treatment) ^[2]			
Anaphylaxis	Y		Y
Systemic Allergic/Hypersensitivity and Non-allergic Reactions	Y		Y

Endpoint / Parameter/ Display Type	Absolute		
	Summary		Individual
	T	F	L
Systemic Allergic/Hypersensitivity Reactions	Y		
Systemic Non-allergic Reactions	Y		
Local Injection Site Reactions	Y		Y
Opportunistic Infections	Y		Y
Malignancies	Y		Y
Serious Cardiac, Vascular and Thromboembolic Events	Y		Y
Serious Ischemic Events	Y		Y
Cardiovascular Events			
All Cardiovascular Events	Y		Y

NOTES:

- T = Table, F = Figures, L = Listings, Y = Display generated, SOC=System Organ Class, PT=Preferred Term.

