10.13.1.5. Safety Tables

Safety : Tables					
No.	Population	IDSL / TST ID / Example Shell	Title	Programming Notes	Deliverable
Exposure					
3.1	ITT	SHELL	Summary of Number of Treatments Administered and Time On-Treatment	See format of Study Population Table 1.28 (200862 'final' reporting effort).	SAC
Adverse Events					
3.2	ITT	SHELL	Overview of All Adverse Events	Add a Total column across all severities	SAC
3.3	ITT	AE1	Summary of All On-Treatment Adverse Events by System Organ Class		SAC
3.4	ITT	AE5	Summary of All On-Treatment Adverse Events by System Organ Class and Maximum Intensity	Add a Total column across all severities	SAC
3.5	ITT	AE1	Summary of All Post-Treatment Adverse Events by System Organ Class		SAC
3.6	ITT	AE5	Summary of All Post-Treatment Adverse Events by System Organ Class and Maximum Intensity	Add a Total column across all severities	SAC
3.7	ITT	AE3	Summary of Common On-Treatment Adverse Events (>=3% in Any Treatment Group) by Overall Frequency	GSK CTR; ≥3% (prior to rounding to nearest percent)	SAC
3.8	ITT	AE1	Summary of All On-Treatment Drug-Related Adverse Events by System Organ Class		SAC
3.9	ITT	AE5	Summary of All On-Treatment Drug-Related Adverse Events by System Organ Class and Maximum Intensity	Add a Total column across all severities	SAC
3.10	ITT	AE1	Summary of Adverse Events Reported on Day of Dosing by System Organ Class		SAC
3.11	ITT	SHELL	Summary of All On-Treatment Adverse Events by Age Group	Add a Total column across all severities	SAC

Safety : Tables					
No.	Population	IDSL / TST ID / Example Shell	Title	Programming Notes	Deliverable
3.12	ITT	SHELL	Summary of On-Treatment Adverse Events by Highest Anti Drug Antibody Result At Any Time Post Baseline		SAC
3.13	ITT	SHELL	Summary of Post-Treatment Adverse Events by Highest Anti Drug Antibody Result At Any Time Post Baseline		SAC
3.14	ITT	AE15	Summary of Number of Subjects and Occurrences of Common non-Serious Adverse Events by System Organ Class and Preferred Term	GSK CTR; $\geq 3\%$ (prior to rounding to nearest percent)	SAC
Serious and Other Significant AEs					
3.15	ITT	AE1	Summary of Fatal Serious Adverse Events		SAC
3.16	ITT	AE1	Summary of Non-Fatal Serious On-Treatment Adverse Events by System Organ Class		SAC
3.17	ITT	AE1	Summary of Non-Fatal Serious Post-Treatment Adverse Events by System Organ Class		SAC
3.18	ITT	AE1	Summary of Serious Adverse Events by System Organ Class (Pre-Treatment)		SAC

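### The treatment-emergent ADA summary has no treatment-boosted category, so a baseline-positive subject whose titre rises on mepolizumab is never counted as treatment-emergent

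*SAP*

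**What the plan says.** Immunogenicity is a safety endpoint in both documents, worded only as "Incidence of immunogenicity" (SAP 2.2; the same in Protocol Section 3). Protocol 9.4.3.2.5 leaves the method to suitable descriptive statistics, so the working definition has to come from SAP 8.2.4.1. That section plans:

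- an ITT table "summarising the number and percentage of negative and confirmed positive subjects ADA samples by treatment group and visit in the ITT population", of which it adds: "The table will also summarise the highest assay result obtained post-baseline for each subject" (Table 3.54);
- a similar table for neutralising antibody (Table 3.56);
- an additional treatment-emergent summary "in the subset of subjects who did not have a positive confirmatory binding antibody assay result prior to the first dose of study treatment" (Table 3.55);
- a listing of all results, in which "titre values, neutralising antibody results and observed mepolizumab concentration) will be listed" (Listing 44).

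On the assay side, the same section says: "Each positive sample from the ADA confirmation assay is serially diluted to provide a titre". Adverse events are also tabulated by antibody status: SAP Table 6 has the row "AEs by Highest Antidrug Antibody Result At Any Time Post Baseline", which becomes Table 3.12, "Summary of On-Treatment Adverse Events by Highest Anti Drug Antibody Result At Any Time Post Baseline", and its post-treatment counterpart, Table 3.13.

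**The concern.** A treatment-emergent antibody response can take two forms: a new antibody in someone who had none, or a rise in one that was already there. Table 3.55 captures the first and excludes the second by construction. The tables that keep baseline-positive subjects classify them by their result after dosing and, as described in the text, not by change from before dosing. An unchanged baseline positive and a boosted one may therefore look the same there.

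At stake is how completely the stated endpoint is reported. Protocol Sections 1 and 2.1 name immunogenicity among the things the study will describe after a direct switch, and Protocol Table 3 says antibodies may alter drug exposure or effect, or cause adverse reactions. If events are few, one or two subjects classified differently move the reported percentage visibly.

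**Working it through.** The plan gives no figure for ADA incidence, baseline positivity, boosting or missing samples, so there is nothing to reproduce. The check is textual, followed by an illustration on assumed counts.

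**Step 1: can a boosted subject enter Table 3.55?** Entry requires no confirmed positive result before the first dose. A boosted subject has one by definition. Neither 8.2.4.1, SAP Table 8 nor the display list gives a titre-rise criterion. The answer is no.

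**Step 2: are the data there?** Yes. A pre-dose sample is scheduled at Visit 2 (Protocol 7.1, 7.2.3 and 7.6), with later samples during treatment and at exit. Every confirmed positive sample is titrated, so a baseline positive has a titre to compare with.

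**Step 3: where does the subject appear?** As confirmed positive by visit and in the highest post-baseline row of Table 3.54, in Tables 3.12 and 3.13, and with titres in Listing 44.

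**Step 4: size.** Assumptions: N = 120 treated (Protocol 4.3), all with valid samples; 6 newly positive; b baseline positives, who all stay positive after dosing. The values 6 and b are not from the documents.

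- Table 3.55: 6/(120 − b)
- Induced plus boosted, if all b boost: (6 + b)/120
- Induced plus boosted, if none boosts: 6/120 = 5.0%
- Highest post-baseline row of Table 3.54, in either case: (6 + b)/120

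| b | Table 3.55 | Induced + boosted, all boost | Induced + boosted, none boosts | Table 3.54 row |
|---|---|---|---|---|
| 0 | 6/120 = 5.0% | 5.0% | 5.0% | 5.0% |
| 1 | 6/119 = 5.0% | 7/120 = 5.8% | 5.0% | 5.8% |
| 3 | 6/117 = 5.1% | 9/120 = 7.5% | 5.0% | 7.5% |
| 6 | 6/114 = 5.3% | 12/120 = 10.0% | 5.0% | 10.0% |

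The Table 3.54 proportion is the same whether every baseline positive boosts or none does.

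A milder set of assumptions takes a 2% induced rate among baseline negatives, half of the baseline positives boosting, and a baseline-positive share p. The combined rate is (1 − p) × 0.02 + p × 0.5. For p = 1%, 5% and 10% this is 2.5%, 4.4% and 6.8%, against 2% in Table 3.55. The boosted subjects left out number 120 × p × 0.5 = 0.6, 3 and 6.

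**Step 5: subjects without a pre-dose result.** Section 8.2.4.1 does not mention them. Its wording, taken literally, admits anyone who lacks a positive result, including a subject with no result. SAP 10.5.2.2 says that when baseline is missing, nothing is derived and the value is set to missing. That is a note under the change-from-baseline and ratio definitions, and the SAP does not say whether it governs this subset. For scale, assume one such subject who is later positive, with 6 new positives among the other 119. Admitting the subject gives 7/120 = 5.8%; leaving the subject out gives 6/119 = 5.0%.

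**The case against.** The strongest reply is that the planned set of outputs is reasonable. New positives among subjects not positive beforehand is an ordinary measure of incidence, and Table 3.55 gives it. SAP 8.2.4.1 calls that summary additional. Baseline positives are shown by visit in Table 3.54, and every titre is listed. Table 3.54 follows a layout from another study, and the shells are held separately (SAP Appendix 14), so its highest-result row may display titres. Numbers should be low: Protocol 4.6.1 describes ADA as infrequent and not linked to negative clinical outcomes, and exclusion criterion 16 removes anyone who received product in an earlier mepolizumab study. All of this stands. It limits the importance of the point but does not supply the missing category.

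Four stronger readings are tempting, and the documents do not support them:

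- *A boosted subject is lost altogether.* Step 3 shows otherwise; the omission is confined to the treatment-emergent count.
- *A missing baseline is treated as negative.* No such rule is stated. The subset wording permits it, and 10.5.2.2 points the other way. It is an ambiguity.
- *A boost would be the signal of the switch from omalizumab.* The assay detects antibody to mepolizumab, and nothing in the documents says that omalizumab induces it.
- *The adverse-event tables are wrong and should be split by treatment-emergent status.* That would put persistently positive subjects with the negatives. Highest post-baseline result is a clearly labelled and defensible way to relate events to the presence of antibody.

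**Conclusion.** The point holds in a limited form. SAP 8.2.4.1 and Table 3.55 define treatment-emergent ADA without a boosted component, so a titre rise in a baseline-positive subject cannot be counted as treatment-emergent, although the data to identify it are collected. Table 3.54 as described cannot be relied on to fill the gap, subject to its unseen shell. The handling of a missing pre-dose result is left open.

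The difference ranges from nil, if nobody is positive at baseline, to 5.3% against 10.0% in the most extreme case shown (6 of 120 positive at baseline, all boosted). Every rate behind that range is assumed. The summary is descriptive in a single-arm study and the effect is probably small. The change is worth making because it is cheap and completes the definition of a stated endpoint.

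**What to change.** In SAP 8.2.4.1 and Table 3.55, report:

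- (a) treatment-induced ADA: a negative pre-dose result and at least one confirmed positive result after baseline;
- (b) treatment-boosted ADA: a confirmed positive pre-dose result and a post-baseline titre above the baseline titre by a stated margin;
- (c) the total of (a) and (b).

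Set the margin from the assay's dilution scheme and precision, which the documents do not give. Two dilution steps would be one example. Use as denominator the ITT subjects with a valid pre-dose result and at least one post-baseline result, and show subjects without a valid pre-dose result in a separate row. Leave Tables 3.12 and 3.13 by highest post-baseline result.

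The cost is a few sentences and one derivation from titres already measured, with no new samples or assays. The one constraint is that the margin must be fixed before database freeze.

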10. APPENDICES

Section	Appendix
RAP Section 4 : Analysis Populations	
Section 10.1	Appendix 1: Protocol Deviation Management and Definitions for Per Protocol Population
RAP Section 5 : General Considerations for Data Analyses & Data Handling Conventions	
Section 10.2	Appendix 2: Time & Events
Section 10.3	Appendix 3: Assessment Windows & Visit Slotting
Section 10.4	Appendix 4: Treatment Phases
Section 10.5	Appendix 5: Data Display Standards & Handling Conventions 
 • Study Treatment & Subgroup Display Descriptors • Baseline Definitions & Derivations • Reporting Process & Standards
Section 10.6	Appendix 6: Derived and Transformed Data 
 • General • Study Population • Efficacy • Safety
Section 10.7	Appendix 7: Premature Withdrawals & Handling of Missing Data 
 • Premature Withdrawals • Handling of Missing Data
Section 10.8	Appendix 8: Values of Potential Clinical Importance 
 • Laboratory Values
Section 10.9	Appendix 9: Multicenter Studies
Section 10.10	Appendix 10: Examination of Covariates and Subgroups
Section 10.11	Appendix 11: Model Checking and Diagnostics for Statistical Analyses
Other RAP Appendices	
Section 10.12	Appendix 12: Abbreviations & Trade Marks
Section 10.13	Appendix 13: List of Data Displays
Section 10.14	Appendix 14: Example Mock Shells for Data Displays

10.1. Appendix 1: Protocol Deviation Management and Definitions for Per Protocol Population

10.1.1. Exclusions from Per Protocol Population

Subjects with protocol deviations considered to potentially have an effect on efficacy will be excluded from the Per Protocol (PP) population. Determination of the Per Protocol population will be performed before the database is frozen. The reason for the exclusion of any subject will be documented.

A subject meeting any of the following criteria will be excluded from the Per Protocol population:

Number	Exclusion Description
01	Inclusion criteria # 2 – Insufficient evidence of asthma for ≥ 2 years that meets the National Heart and Lung Institute guidelines or GINA guidelines
02	Inclusion criteria # 3 – No persistent airflow obstruction as indicated by For subjects ≥ 18 years of age at Visit 1, a pre-bronchodilator FEV1 $< 80\%$ predicted [Quanjer, 2012] recorded at Visit 1. For subjects 12-17 years of age at Visit 1, a pre-bronchodilator FEV1 $< 90\%$ predicted [Quanjer, 2012] OR FEV1/FVC ratio < 0.8 recorded at Visit 1.
03	Inclusion criteria # 4 – No eosinophilic airway inflammation as defined by: 
 Peripheral blood eosinophil level of ≥ 300 cells/μL that is related to asthma demonstrated in the 12 months prior to visit 1 OR Peripheral blood eosinophil level of ≥ 150 cells/μL demonstrated at Visit 1 that is related to asthma
04	Inclusion criteria # 5 – Absence of evidence of a well-documented requirement for regular treatment with high dose ICS (equivalent to $\geq 880\mu\text{g}/\text{day}$ fluticasone propionate (FP) (ex-actuator) or equivalent daily in adults and $\geq 440\mu\text{g}/\text{day}$ FP (ex-actuator) or equivalent daily for subjects aged 12-17) in the 12 months prior to Visit 1 [Note: For ICS/LABA combination preparations, the highest approved maintenance dose in the local country will meet this ICS criterion.]
05	Inclusion criteria # 6 – Absence of current treatment with an additional controller medication, besides ICS, for at least 3 months or a documented failure in the past 12 months of an additional controller medication for at least 3 successive months [e.g., long-acting beta-2-agonist (LABA), leukotriene receptor antagonist (LTRA), or theophylline]
06	Inclusion criteria # 7 – Asthma symptoms not uncontrolled at Visit 1, as defined by an ACQ-5 score of < 1.5 .
07	Inclusion criteria # 8 – Not receiving Omalizumab treatment based on weight and IgE levels, for at least the 4 months prior to Visit 1.
08	Inclusion criteria # 9 – No history of two or more exacerbations requiring treatment with systemic corticosteroids (intramuscular, intravenous, or oral) in the 12 months prior to Visit 1 despite the use of high-dose ICS. [Note: For subjects receiving omalizumab for ≥ 8 months, at least one exacerbation must have occurred while on omalizumab treatment. For subjects receiving maintenance oral corticosteroids, the corticosteroid treatment for the exacerbations must have been a two-fold dose increase or greater.]
09	Continuation to treatment criteria # 1 – Asthma symptoms not uncontrolled at Visit 2, as

Number	Exclusion Description
	defined by an ACQ-5 score of <1.5.
10	Continuation to treatment criteria # 2 – Subjects who experience an asthma exacerbation during run-in who have not returned to their baseline asthma status within one week of Visit 2.
11	Continuation to treatment criteria # 3 – Any subject with changes in the dose or regimen of ICS, and/or additional controller medication (except for treatment of an exacerbation) during the run-in period.
12	Continuation to treatment criteria # 4 – Subjects who do not receive their last dose of Omalizumab during the correct period, as defined by: 
 For subjects receiving omalizumab every 4 weeks, their last dose is received <3 or >5 weeks prior to Visit 2. For subjects receiving omalizumab every 2 weeks, their last dose is received <1 or >3 weeks prior to Visit 2.
13	Any subject with changes in the dose or regimen of baseline ICS, and/or additional controller medication during open-label treatment. N.B. This excludes the use of OCS for the treatment of an asthma exacerbation.
14	Use of any prohibited medication during the study [1].
15	Receiving the incorrect study treatment at any point during the study.

NOTES:

- [1] See Protocol Section 6.8.2 for the list of prohibited medications within this study.

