**Figure 1 Study Design**

## 4.2. Treatment Arms and Duration

Eligible patients will receive mepolizumab 100 mg SC every 4 weeks for 28 weeks and will be requested to participate in the study for a maximum of 38 weeks (Visit 0 to the Exit Visit (Visit 10), inclusive as described in [Table 2](#)).

**Table 2** Study phases

Phase	Phase Title	Duration	Description
1	Pre-screening	0 to 2 weeks	At the Pre-screening Visit, details about the study and procedures will be explained through the informed consent process. The Pre-screening Visit (Visit 0) can occur on the same day as the Screening Visit (Visit 1) but must be completed prior to initiating any Visit 1 procedures.
2	Screening / Run-in	1 to 4 weeks	Subjects who meet all the eligibility criteria at Screening, will enter the run-in period for a minimum of 1 week and a maximum of 4 weeks in order to continue to assess the subject's eligibility for the study. Subjects who experience an asthma exacerbation during the run-in period should receive treatment for their exacerbation and remain in the run-in period until the investigator considers that the subject has returned to their baseline asthma status for at least one week. Those subjects that are not eligible to continue in the study at the end of the 4 week run-in period will be deemed run-in failures (see Section 5.4 ).
3	Treatment	32 weeks	At Visit 2 (Week 0) those subjects who successfully complete the run-in period as well as meet the other pre-defined eligibility and continuation to treatment criteria (see Section 5.3 ) will receive mepolizumab 100 mg SC every 4 weeks for a total of 8 doses.  The treatment period will conclude with subjects completing Exit Visit (Visit 10) assessments approximately 4 weeks after the subject was administered their last dose of study treatment at Visit 9.

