**REQUIRED CRITERIA TO START TREATMENT**

1. **Not optimally controlled:** An ACQ-5 score of  $\geq 1.5$  recorded at Visit 2
2. **No Asthma Exacerbation:** Subjects with an ongoing asthma exacerbation at Baseline (Visit 2) should have their Visit 2 delayed until the investigator considers the subject has returned to their baseline asthma status for at least one week. If the 4-week screening/run-in period has elapsed and subjects have not returned to their baseline asthma status, then they should be considered a run-in failure. An exacerbation is defined as worsening of asthma requiring the use of systemic corticosteroids and/or emergency department visit, or hospitalisation (see Section 7.3.2.4 Clinically Significant Asthma Exacerbation).
3. **Maintenance Asthma Therapy:** No changes in the dose or regimen of ICS and/or additional controller medication (except for treatment of an exacerbation) during the run-in period.
4. **Last dose of omalizumab:** For subjects receiving omalizumab every 4 weeks, their last dose must be 3 to 5 weeks prior to Visit 2. For subjects receiving omalizumab every 2 weeks, their last dose must be between 1 to 3 weeks prior to Visit 2.

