**Instructions for completing the questionnaires can be found in the SRM.**

##### **7.3.2.1.1. Asthma Control Questionnaire (ACQ)**

The ACQ-5 is a five-item questionnaire, which has been developed as a measure of subject' asthma control that can be quickly and easily completed [[Juniper 1999](#); [Juniper, 2005](#)]. The questions are designed to be self-completed by the subject. The five questions (concerning nocturnal awakening, waking in the morning, activity limitation, shortness of breath and wheeze) enquire about the frequency and/or severity of symptoms over the previous week. The response options for all these questions range from zero (no impairment/limitation) to six (total impairment/ limitation) scale ( see [Appendix 8](#))

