### **Per Protocol (PP) Population**

The Per Protocol (PP) population will consist of all subjects in the Intent-to-Treat population who have not been identified as full protocol deviators with respect to criteria that are considered to impact the primary efficacy analysis. The decision to exclude a subject from the PP population or exclude part of their data from the PP population analyses will be made prior to freezing the study database. The PP population will be used for a supplementary analysis of the primary endpoint.

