10.5.2. Baseline Definition & Derivations

10.5.2.1. Baseline Definition

- Baseline will be defined for all subjects who are within the ITT population.
- For all endpoints the baseline values for each assessment will be the latest available assessment prior to first dose of mepolizumab.
- Measurements on the same date as the first administration of mepolizumab will be considered within the baseline derivation if measurement time is not captured. Where the measurement time is captured this should be compared against the time of first receiving mepolizumab.

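### SAP Per Protocol exclusion 10 does not reproduce the one-week recovery rule it cites and, read plainly, keeps subjects who recovered fewer than 7 days before Visit 2

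*SAP*

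**What the plan says.** Protocol Table 2 (Section 4.2) covers any exacerbation during run-in. Such subjects are to be treated and to "remain in the run-in period until the investigator considers that the subject has returned to their baseline asthma status for at least one week". Protocol 5.3, criterion 2, covers an exacerbation still ongoing at Visit 2: those subjects "should have their Visit 2 delayed until the investigator considers the subject has returned to their baseline asthma status for at least one week". Both passages set a minimum duration of recovery.

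SAP 10.1.1, exclusion 10, is labelled as continuation criterion 2. It removes from the Per Protocol set: "Subjects who experience an asthma exacerbation during run-in who have not returned to their baseline asthma status within one week of Visit 2".

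Three other passages bear on the point:

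- Protocol 7.3.2.1.1: the ACQ-5 questions "enquire about the frequency and/or severity of symptoms over the previous week".
- SAP 10.5.2.1: "the baseline values for each assessment will be the latest available assessment prior to first dose of mepolizumab". This is normally the Visit 2 value.
- Protocol 9.3.1: "The PP population will be used for a supplementary analysis of the primary endpoint". The primary population is ITT.

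**The concern.** The protocol's one-week recovery period has the same length as the ACQ-5 recall period. If it is observed, the baseline score describes a week that lies wholly after recovery. Exclusion 10 loses the minimum duration. A subject who recovered shortly before Visit 2 breaks the criterion but has, in ordinary language, recovered within a week of Visit 2, and so is not excluded.

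The study has a single arm and every comparison is made back to baseline. If the baseline score is raised by a recent exacerbation, the natural return from it counts as improvement after the switch, and no control arm cancels it. The Per Protocol set is meant to remove deviations that could influence the primary efficacy analysis, and this deviation acts on the baseline score itself.

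**Working it through.** The plan states no figure on this point, so the check compares the two rules by day.

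Let d be the number of days from return to baseline asthma status to Visit 2 (positive means before Visit 2).

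- Protocol rule: met if d ≥ 7.
- Recall days not at baseline status = min(7, max(0, 7 − d)).
- SAP exclusion 10, four possible readings. A: kept if recovered by Visit 2 (d ≥ 0). B: kept if recovered by one week after Visit 2 (d ≥ −7). C: kept if recovery falls within 7 days either side of Visit 2 (−7 ≤ d ≤ 7). D: shorthand for the protocol rule (kept if d ≥ 7).

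| d | Protocol rule met | Recall days affected | A | B | C | D |
|---|---|---|---|---|---|---|
| −3 | no | 7 | out | kept | kept | out |
| 0 | no | 7 | kept | kept | kept | out |
| 1 | no | 6 | kept | kept | kept | out |
| 3 | no | 4 | kept | kept | kept | out |
| 6 | no | 1 | kept | kept | kept | out |
| 7 | yes | 0 | kept | kept | kept | kept |
| 10 | yes | 0 | kept | kept | out | kept |

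Under A, B and C, subjects who recovered 0 to 6 days before Visit 2 stay in although they broke the rule. Reading C also removes compliant subjects who recovered more than 7 days before. Only D agrees with the protocol, and the words do not say it.

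Elsewhere in the SAP:

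- None of the other 14 numbered exclusions covers this deviation. Exclusion 09 removes only Visit 2 scores below 1.5, and exacerbation symptoms push the score the other way.
- SAP Table 1, which lists changes from the protocol's analysis, does not mention it.
- The neighbouring exclusion 12 negates its criterion exactly, with numerical limits on both sides. This suggests that the wording of exclusion 10 is a slip.

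Size, for illustration only. From Protocol 9.2.1, 120 treated with 15% withdrawal gives 120 × 0.85 = 102 subjects with Week 32 data. Assume that k of them are affected, each with baseline ACQ-5 raised by r points. Neither k nor r is in the documents. Shift in mean change = −k × r / 102.

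- k = 2, r = 0.5: −0.010
- k = 5, r = 0.5: −0.025
- k = 5, r = 1.0: −0.049
- k = 10, r = 1.0: −0.098

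The shift is always towards apparent improvement.

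**The case against.** The strongest reply is that exclusion 10 names continuation criterion 2, so its time phrase may be loose shorthand for the protocol rule (reading D). If so, there is no gap in intent. That is possible, but the list is what will be applied, and the line then still needs correcting.

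Second, other provisions might catch these subjects. SAP 10.1.1 opens with a general rule: "Subjects with protocol deviations considered to potentially have an effect on efficacy will be excluded from the Per Protocol (PP) population". SAP 4.1 requires a review of deviations before freeze, and Table 1.4 in the display list reports failed continuation criteria within the ITT population. So it is not certain that such a subject would be kept. The numbered list, however, defines the exclusions and gives the wrong answer when followed literally.

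Third, numbers should be small. The protocol requires Visit 2 to be delayed and allows no deviations from the continuation criteria. This stands.

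Some stronger readings are tempting but not supported:

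- A reader might infer that the primary result is biased by this line. It is not: these subjects are in the ITT analysis whatever exclusion 10 says. For the same reason the shift should not be set against the planning margin between −0.55 and −0.74, which concerns the primary analysis.
- A reader might take the Per Protocol analysis to be the only supporting analysis of the primary endpoint. SAP 7.1.2 also lists historical-placebo comparisons and subgroup analyses.
- A reader might conclude that subjects who recover after Visit 2 are kept. Readings B and C allow this, but they are strained, because the criterion is assessed at Visit 2.
- Nothing in the documents ranks this deviation above the others listed, such as controller changes during treatment.

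**Conclusion.** The mismatch is real, and the line is wrong as written. Exclusion 10 cites a criterion with a minimum duration of recovery and replaces it with closeness to Visit 2. On its plain reading it keeps subjects who recovered fewer than 7 days before Visit 2, with between 1 and 7 of the 7 baseline recall days preceding recovery. The bias in the Per Protocol change from baseline is towards improvement.

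The consequence is minor. It is confined to a supporting analysis. The illustrative shift of about 0.01 to 0.10 points rests on assumed values (2 to 10 affected subjects among 102, each raised by 0.5 to 1.0) and is not a bound. With good adherence to the delay rule, few or no subjects would be affected. The case for acting is that membership of the Per Protocol set should follow the protocol and be reproducible.

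**What to change.** Before database freeze, reconcile SAP 10.1.1 exclusion 10 with the criterion it cites. For example: exclude subjects with a run-in exacerbation who did not meet the protocol's requirement of at least one week back at baseline asthma status before Visit 2.

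State how this will be determined. The protocol leaves recovery to the investigator's judgement, so use that judgement where it is recorded. Otherwise use the recorded exacerbation end date and the Visit 2 date, and say that the end date is a proxy: the documents show no recorded date of return to baseline status.

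The cost is one line in SAP Appendix 1 and, with that proxy, no new data collection. A few subjects may leave the Per Protocol set. The change concerns only the analysis set and takes no position on the clinical rule.
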